## 2. Objectives

Our primary aim is to determine the effect of ketorolac administration on total postoperative morphine dosage required to achieve analgesia in children with OSA undergoing adenotonsillectomy. Our secondary aim will be to characterize the effect of intra-operative ketorolac administration on FLACC pain scores and PACU recovery time. The measures we will monitoring are PACU morphine requirements, FLACC pain scores, PACU recovery time, incidence of post-tonsillectomy bleeding and total amount of pain medications administered during hospitalization.

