## **6. Procedures Involved**

After consent has been obtained, patients will be randomly assigned to ketorolac group or non-ketorolac group. All patients will receive a similar anesthetic with inhalational induction with the exception of the ketorolac group receiving 0.5mg/kg IV ketorolac at the end of the procedure once hemostasis has been achieved. The PACU nurses, who will be blinded to ketorolac administration, will evaluate the patients using FLACC scores at 10 minutes post-op, 20 minutes post-op and at time of PACU discharge. For patients with a FLACC score of 6-10, morphine 0.05mg/kg will be administered. For patients with FLACC scores of 3-5, morphine 0.025mg/kg will be administered. The total amount of opioid required to obtain a FLACC score of less than 3 will be evaluated as the primary outcome. The secondary outcomes to be evaluated will be PACU FLACC scores, time required in PACU, incidence of post-tonsillectomy bleeding and total pain medications administered during hospital admission.

All patients will undergo inhalational induction with Nitrous Oxide and Sevoflurane. After IV placement, propofol 1-3mg/kg and fentanyl 1mcg/kg will be administered prior to intubation. Immediately after induction, dexamethasone 0.5mg/kg and an IV infusion of acetaminophen 15mg/kg will be administered. During the intra-op course, dexmedetomidine 0.5mcg/kg and odansetron 0.1mg/kg will be given. Patients in the ketorolac group will receive 0.5mg/kg IV, while those in the non-ketorolac group will not receive any.

A rescue dose of Fentanyl 0.5-1mcg/kg IV will be available for administration at the end of the procedure. The decision to administer this will be left to the discretion of the attending anesthesiologist for the case. The choice to give this will be made based on variables including patient's condition and a 20% increase in the heart rate and blood pressure. In PACU, nurses will be blinded to ketorolac administration, but will be informed of all other medications given.

---

**Protocol Title:** Ketorolac as a Strategy for Reducing Post-Operative Opioid Requirement in Children with OSA undergoing Adenotonsillectomy: A Randomized Controlled Trial

---

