The PACU nurses will evaluate the patients using FLACC scores at 10 minutes post-op, 20 minutes post-op and at time of PACU discharge. For patients with a FLACC score of 6-10, morphine 0.05mg/kg will be administered. For patients with FLACC scores of 3-5, morphine 0.025mg/kg will be administered. For patients with FLACC scores of 0-2, no morphine will be administered. The total amount of morphine required to obtain a FLACC score of less than 3 will be recorded.

The PACU length of stay will be monitored as a secondary outcome, as decreasing the PACU length of stay may also be a benefit of ketorolac administration. In addition, we will monitor for post-tonsillectomy bleeding and categorize as either post-tonsillectomy bleeding requiring surgical intervention or post-tonsillectomy bleeding not requiring surgical intervention. In addition, the total amount of pain medication required during hospitalization will be evaluated. Once the patient is discharged, there will be no further collection of data or follow-up with the participant.

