## **7. Statistical Analysis Plan**

Descriptive statistics will be calculated for all variables of interest and will include means and standard deviations, medians and ranges, or counts and percentages, as appropriate. Characteristics of subjects who received ketorolac will be compared to those who did not receive ketorolac using Chi-square tests for comparisons of categorical variables (i.e. gender, race, etc.) and two-sample tests or Mann-Whitney tests for continuous variables (i.e. age, apnea hypopnea index, etc.). For binary outcomes, such as post-tonsillectomy bleeding, cohorts will be compared using Chi-square tests. Generalized linear models will be used to compare differences in amount of narcotic among the two tonsillectomy cohorts, adjusting for any differences in patient and surgical characteristics that may exist between the two groups. Statistical significant will be performed using Stata v. 13.1 (College Station, TX).

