## **19. Provisions to Monitor the Data to Ensure the Safety of Participants**

Monitoring of Adverse Events (AEs) and Serious Adverse Events (SAEs) is an important aspect of data collection. After enrollment, the principal investigator or designee will collect the adverse experiences from the medical record. The study subjects will be reviewed on a case-by-case basis. The principal investigator will determine the seriousness of each adverse event and

whether or not the event was related to the study. Serious adverse events (life-threatening, requiring intervention) will be reported to the IRB within the guidelines set by the IRB.

After 50% of patients enrolled have undergone surgery, evaluation of the rates of post-tonsillectomy bleeding will be carefully evaluated. If any significant increase is noted, the study will be evaluated by the principal investigator for possible discontinuation.

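### Bleeding is a secondary outcome and the subject of the halfway safety review, yet data collection stops at discharge, so later bleeds go uncounted

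*Combined protocol and SAP*

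**What the plan says.** Section 2 lists among the monitored measures "incidence of post-tonsillectomy bleeding and total amount of pain medications administered during hospitalization". Section 6 names as secondary outcomes "incidence of post-tonsillectomy bleeding and total pain medications administered during hospital admission". In both places the reference to the hospital stay follows the pain-medication total and is not clearly applied to bleeding. Section 6 will also "categorize as either post-tonsillectomy bleeding requiring surgical intervention or post-tonsillectomy bleeding not requiring surgical intervention", and Section 7 states: "For binary outcomes, such as post-tonsillectomy bleeding, cohorts will be compared using Chi-square tests".

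The same paragraph of Section 6 that sets out the bleeding categories ends with "Once the patient is discharged, there will be no further collection of data or follow-up with the participant". Section 23 says the same and specifies discharge from the hospital. Sections 1 and 9 give one day of participation.

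Section 19 says: "After enrollment, the principal investigator or designee will collect the adverse experiences from the medical record". It gives no end date. It adds: "Serious adverse events (life-threatening, requiring intervention) will be reported to the IRB within the guidelines set by the IRB". It then plans a halfway look: "After 50% of patients enrolled have undergone surgery, evaluation of the rates of post-tonsillectomy bleeding will be carefully evaluated". A significant increase would lead the principal investigator to consider discontinuing the study.

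**The concern.** The outcome carries a general name and no window, while the collection rule stops at the hospital door. A bleed after discharge, including one that needs surgery, falls outside the outcome as it would be collected, although it fits the name and one of the two categories.

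Two things are at stake. First, Section 3 gives post-operative bleeding as the continuing worry about ketorolac. A count cut off at discharge but reported under the general name could be read as reassurance that the data do not give. Second, the halfway review is the only planned interim look at safety and may lead to discontinuation. Whether it sees post-discharge bleeds depends on whether staff follow Section 19 or Sections 6 and 23.

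**Working it through.** **The text, side by side**

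| Point | Sections 6 and 23 | Section 19 |
|---|---|---|
| When collection ends | At discharge | Not stated |
| Source | Not stated for bleeding | Medical record, for adverse events in general |
| Bleed at home leading to surgery | Not collected | Could be a reportable serious event |
| Source and window for the halfway review | Not stated | Not stated |

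A post-discharge bleed needing surgery could thus be reportable under one section and uncollected under another. This finding needs no arithmetic.

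**Size, for illustration**

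The plan states no figure for the bleeding comparison or the halfway review, and gives no inputs behind the sample size of 120, so there is nothing to reproduce first.

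Inputs:
- Bleeding risk *p* = 2% (children with OSA) and 3% (after tonsil removal), from Section 15, which states no time window.
- *N* = 120, from Section 12.
- Halfway *n* = 0.5 × 120 = 60. This is an assumption, since Section 19 refers to half of the patients enrolled.
- Share of bleeds that occur before discharge, *f*. This is not in the documents and is varied as an assumption.

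Formulas:
- Expected bleeds in all: 120 × 0.02 = 2.4 and 120 × 0.03 = 3.6.
- Expected after discharge: 120 × p × (1 − f).
- Chance that at least one falls after discharge: 1 − (1 − p(1 − f))^120.
- Chance that none is recorded: (1 − pf)^120, and (1 − pf)^60 at halfway if the review uses pre-discharge data only.

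Worked example, f = 0.8 and p = 0.02:
- Expected after discharge: 120 × 0.02 × 0.2 = 0.48.
- At least one missed: 1 − 0.996^120 = 0.382.
- None recorded in 120: 0.984^120 = 0.144.
- None recorded in 60: 0.984^60 = 0.380.

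Ranges below cover the two values of *p*.

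| f | Expected after discharge | At least one missed in 120 | None recorded in 120 | None recorded in 60 |
|---|---|---|---|---|
| 100% | 0 | 0% | 3-9% | 16-30% |
| 80% | 0.48-0.72 | 38-51% | 5-14% | 23-38% |
| 50% | 1.2-1.8 | 70-84% | 16-30% | 40-55% |
| 10% | 2.16-3.24 | 89-96% | 70-79% | 84-89% |

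**Power for bleeding with full capture**

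The plan states neither the allocation ratio nor alpha, so equal arms and two-sided 0.05 are assumed. Enumerating all outcomes of the uncorrected chi-square test with 60 per arm, power to detect a doubling is 0.072 (2% against 4%) and 0.109 (3% against 6%). With 30 per arm at halfway it is 0.018 and 0.046. For 80% power the trial would need about 1,141 or 749 per arm.

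**The case against.** The strongest reply is that the documents do set a window. Section 6 describes bleeding surveillance and ends data collection in one paragraph, Section 23 agrees, and participation is one day. On this reading the outcome is bleeding before discharge under a broad label. That is a reasonable reading, but it confirms the cut-off rather than removing it, and the name and Section 19 would still need to be brought into line.

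It can also be said that Section 19 already names the medical record as its source, and that its wording fixes a start and says nothing about the period after discharge. This is partly right: the record is named for adverse events in general, and using it for the halfway review would be natural. But the section neither ties that source to the bleeding review nor says how far it runs.

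The illustrative figures rest on a share that the documents do not give, and the 2-3% has no stated window. If that risk already refers to the hospital stay, multiplying it by *f* is wrong and the table does not apply. This stands, and the finding should not be rated on those percentages.

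Finally, bleeding lies outside the stated primary and secondary aims, and power is low in any case. That also stands. Longer capture would not make the between-arm comparison informative. It would make the count complete enough to match its name, and give the halfway review the events it is meant to notice.

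**Conclusion.** The point holds. As written, bleeds after discharge are excluded from an outcome whose name includes them, and the plan does not say whether the halfway review would see them. The recorded incidence can only equal or understate the total, so the trial cannot support a statement about overall post-tonsillectomy bleeding.

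The amount missed cannot be determined from the documents. It is modest if most bleeds occur before discharge and large if few do. The percentages assume that the Section 15 risk covers the whole post-operative period and that 60 children are reviewed at halfway; the textual finding depends on neither.

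The total morphine outcome, FLACC scores and PACU time are unaffected. This should be corrected, but it does not threaten the trial's main result.

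**What to change.** Preferred change: amend Sections 6, 9 and 23, and reconcile Section 19, so that study staff review the Epic record in both arms for return visits, readmissions and re-operations for bleeding over a fixed post-operative window set by the investigators. Name that review as the data source for the halfway look, apply the same window, and state how many children have not yet completed it. Report bleeding before discharge and over the full window separately by assigned arm, with exact confidence intervals and a statement that the trial is not powered for bleeding.

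The cost is an amendment, consent wording and a short review of 120 charts at one centre, with no added visits or procedures. Staff time is assumed to be available: Section 24 covers training only, and Section 22 mentions budget restrictions in another context. Bleeds treated elsewhere would still be missed, and power would stay low.

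Alternative, if no post-discharge data will be collected: rename the outcome *bleeding before hospital discharge*, state in Section 19 that adverse-event collection and the halfway review cover only that period, and limit conclusions to it. This costs only wording, but the halfway review would remain blind to later bleeds.

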## **7. Statistical Analysis Plan**

Descriptive statistics will be calculated for all variables of interest and will include means and standard deviations, medians and ranges, or counts and percentages, as appropriate. Characteristics of subjects who received ketorolac will be compared to those who did not receive ketorolac using Chi-square tests for comparisons of categorical variables (i.e. gender, race, etc.) and two-sample tests or Mann-Whitney tests for continuous variables (i.e. age, apnea hypopnea index, etc.). For binary outcomes, such as post-tonsillectomy bleeding, cohorts will be compared using Chi-square tests. Generalized linear models will be used to compare differences in amount of narcotic among the two tonsillectomy cohorts, adjusting for any differences in patient and surgical characteristics that may exist between the two groups. Statistical significant will be performed using Stata v. 13.1 (College Station, TX).

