## **12. Local Number of Participants**

We will enroll a total of 120 participants for this study.

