## **15. Risk to Participants**

The drug that is being tested may not work any better than regular care. 1-10% of patients that take Ketorolac may have:

- Nausea
- Abdominal Pain
- Headaches

Serious, less common risks include:

- Post-procedure bleeding, after tonsil removal (3%), in children with OSA (2%)
- Less than (1%): chance of allergic or anaphylactic reaction.

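### A Chi-square test alone tells almost nothing about bleeding at 120 patients; Section 7 should pre-specify a risk difference with a 95% interval

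*Combined protocol and SAP*

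**What the plan says.** Section 6 lists bleeding among the secondary outcomes: "incidence of post-tonsillectomy bleeding and total pain medications administered during hospital admission". It also sorts bleeds by whether they need surgical intervention, and it ends data collection at discharge.

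Section 7 sets the analysis: "For binary outcomes, such as post-tonsillectomy bleeding, cohorts will be compared using Chi-square tests". For all variables of interest, the descriptive output "will include means and standard deviations, medians and ranges, or counts and percentages, as appropriate". Section 7 gives no risk difference, confidence interval, exact test, small-cell rule, continuity-correction rule, significance level or sidedness.

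On size, Section 12 says "We will enroll a total of 120 participants for this study". On allocation, Section 6 says only that "patients will be randomly assigned to ketorolac group or non-ketorolac group", with no ratio. Section 15 gives the only bleeding rates: "Post-procedure bleeding, after tonsil removal (3%), in children with OSA (2" (the second figure is 2%).

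Section 19 adds a review of bleeding rates once half of the patients have had surgery: "If any significant increase is noted, the study will be evaluated by the principal investigator for possible discontinuation". It names no test and no threshold.

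**The concern.** Bleeding is the reason for caution about ketorolac that the Background gives, and it is a declared secondary outcome. The plan offers one inferential statement about it, a Chi-square p-value, for an event expected once or twice per arm. With so few events, the p-value will probably be non-significant whether or not ketorolac raises the bleeding rate. Without a pre-specified interval, nothing in the planned output shows how large an increase remains compatible with the data. What is at stake is the bleeding conclusion; the primary morphine comparison is not affected.

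**Working it through.** **Inputs.** Total 120 (Section 12). Bleeding rate 2% in children with OSA and 3% after tonsil removal (Section 15). Assumed because not stated: 1:1 allocation (60 per arm), two-sided 5% level, no continuity correction. The plan gives no power calculation, so there is no figure of its own to reproduce.

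**Expected bleeds** = patients x rate.
- 60 per arm: 60 x 0.02 = 1.2 and 60 x 0.03 = 1.8.
- 50% review, 30 per arm: 0.6 and 0.9.
- If allocation were 1:2: 40 x 0.02 to 40 x 0.03 = 0.8 to 1.2 in the smaller arm, and 80 x 0.02 to 80 x 0.03 = 1.6 to 2.4 in the larger.

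The customary minimum of 5 expected per cell needs at least 10 bleeds in total. The binomial chance of that among 120 is 0.02% at a 2% rate and 0.3% at 3%. The chance of no bleed at all is 0.98^120 = 8.9% or 0.97^120 = 2.6%. In that case the Chi-square statistic cannot be computed.

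**Size and power.** These come from summing the two binomial distributions over every table with p < 0.05, at 60 per arm. Each range runs from a base rate of 2% to one of 3%.

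| | Chi-square | Fisher |
|---|---|---|
| True size at nominal 5% | 1.9% to 3.5% | 0.08% to 0.3% |
| Power, risk doubled | 7% to 11% | 1.1% to 3.3% |
| Power, risk tripled | 18% to 27% | 5.5% to 13.8% |

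**Sample size for 80% power to detect a doubling** (normal approximation). With p the mean of the two rates:

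n per arm = [1.96 x sqrt(2p(1-p)) + 0.842 x sqrt(p1(1-p1) + p2(1-p2))]^2 / (p2-p1)^2

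- 2% v 4%: (0.473 + 0.203)^2 / 0.0004, about 1,141 per arm.
- 3% v 6%: (0.575 + 0.246)^2 / 0.0009, about 749 per arm.

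So low power comes from the sample size, not from the choice of test.

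**Dependence on the test: 4 v 0 bleeds.** Chi-square = 120 x (4 x 60 - 0 x 56)^2 / (60 x 60 x 4 x 116) = 4.14, p = 0.042. The other p-values are Barnard 0.045, Boschloo 0.083, Fisher 0.119 and continuity-corrected Chi-square 0.127.

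**What an interval would show** (Newcombe's score-based 95% limits for the risk difference).
- 0 v 0: the Wilson upper limit per arm is 3.84 / (60 + 3.84) = 6.0%, so the difference runs from -6.0 to +6.0 points.
- 1 v 1: the Wilson limits for 1/60 (1.67%) are 0.29% and 8.86%. The half-width is sqrt(1.37^2 + 7.19^2) = 7.3, giving -7.3 to +7.3 points.
- 2 v 1: -5.9 to +9.8 points.

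Set against a base rate of 2-3%, an upper limit of +7.3 points leaves open a rate of (2 + 7.3)/2 = 4.7 times or (3 + 7.3)/3 = 3.4 times the base. A p-value does not convey that.

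**The case against.** The strongest reply is that the Chi-square test is not doing harm. Its true size stays below 5%, and for 4 v 0 it agrees closely with Barnard's exact test; Fisher and the continuity-corrected version are the conservative outliers. Fisher, the usual replacement, would make a safety comparison even less sensitive. All of this stands. A reader might infer from the small counts that false-positive bleeding signals are inflated, and the enumeration does not support that. The exact tests also disagree among themselves for 4 v 0, so asking for an exact test without naming one would settle nothing.

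Several other stronger readings also go beyond the text.
- A reader might infer that the investigators intend to treat non-significance as proof of safety. No section says so, and there is no bleeding margin or non-inferiority claim. The mention of safety in Section 4 concerns the institution's current standard regimen.
- A reader might infer that the Chi-square test governs the half-way review. Section 19 names no test, and its wording could mean a clinically notable increase.
- A reader might infer that the two severity classes will be tested on still sparser tables. Section 6 only categorises them, and Section 7 plans no test by class.
- A reader might infer that no estimate is planned. Counts and percentages are planned, so anyone could derive an interval later; what is missing is a pre-specified one.
- A reader might infer that bleeding ranks as the chief question. The Background calls it a concern, and it is one of several secondary outcomes.

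None of this removes the core point: the only planned inference on bleeding is a p-value that is uninformative when non-significant.

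**Conclusion.** The concern holds in a limited form. With 1.2-1.8 bleeds expected per arm, a lone Chi-square test would miss a doubling of bleeding in 89-93% of trials and a tripling in 73-82%. The fault is the absence of a pre-specified interval and of a stated basis for the conclusion; it is not an inflated error rate. Changing the test alone would gain little.

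The figures rest on 1:1 allocation, a two-sided 5% level, no continuity correction and the rates in Section 15. Those rates stand in the ketorolac risk list, so they may be background or on-drug rates; the conclusion is the same either way. The expected counts are probably upper bounds, because bleeds after discharge are not collected. This is a cheap improvement to one secondary outcome.

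**What to change.** In Section 7:

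1. Make the main bleeding summary the risk difference, ketorolac minus no ketorolac, with a 95% score or exact interval. Name the method and choose one that can be computed when an arm has no bleeds (Newcombe's can).
2. State that the bleeding conclusion rests on the upper limit of that interval, and that a non-significant result is not evidence of safety.
3. If a p-value is kept, replace Chi-square with one unconditional exact test named in advance, Barnard or Boschloo. Do not substitute Fisher, whose power is about 1-3% for a doubling and 5-14% for a tripling.
4. Give counts by surgical and non-surgical class descriptively, without a test.

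In Section 19, have the 50% bleeding review report the same risk difference and interval.

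The cost is a few sentences and a little more analysis, with no added patients, visits or data. The downside is a wide interval that makes the safety statement less favourable. The change does not raise power; it shows openly what 120 patients can and cannot rule out.

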## **10. Inclusion and Exclusion Criteria**

### **Inclusion Criteria:**

- Patients 2 years old through 18 years of age
- Diagnosis of sleep disordered breathing or obstructive sleep apnea
- Children undergoing elective tonsillectomy or adenotonsillectomy at Children's Healthcare of Atlanta Egleston location
- Parent or legal guardian willing to participate, and able to understand and sign the provided informed consent
- No known coagulation defect

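### The primary-outcome model adjusts for whatever differs between the randomised arms, instead of for a baseline covariate set fixed in advance

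*Combined protocol and SAP*

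**What the plan says.** Section 6 (Procedures Involved) randomises children after consent: "After consent has been obtained, patients will be randomly assigned to ketorolac group or non-ketorolac group". It also defines the main endpoint: "The total amount of opioid required to obtain a FLACC score of less than 3 will be evaluated as the primary outcome".

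Section 7 is the whole statistical plan. It first describes significance tests comparing characteristics between children who did and did not get ketorolac: chi-square tests for categorical variables, and "two-sample tests or Mann-Whitney tests for continuous variables (i.e. age, apnea hypopnea index, etc" for continuous ones. Both lists of examples are open-ended. It then gives one model for narcotic amount, a generalized linear model "adjusting for any differences in patient and surgical characteristics that may exist between the two groups". Nothing else in the document bears on covariates for the primary outcome.

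Two other places matter. In Section 6, fentanyl may be given at the end of the procedure, and "The decision to administer this will be left to the discretion of the attending anesthesiologist for the case". Section 10 admits children on "Diagnosis of sleep disordered breathing or obstructive sleep apnea", with no sleep study required.

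**The concern.** In a correctly randomised trial, baseline differences between arms arise by chance. The reason to adjust is that a covariate predicts the outcome, not that it happened to be unbalanced. A rule keyed to observed differences has three consequences:

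- **Precision.** A strong predictor that balances well is dropped, and the precision it would have bought is lost.
- **Discretion.** With no list and no threshold, two analysts could each follow Section 7 exactly and fit different primary models. If the choice is made after results are seen, the nominal 5% error rate is no longer assured.
- **Timing.** Surgical characteristics are not confined to facts known before randomisation. The wording permits, but does not require, adjustment for something that happened afterwards, such as the discretionary fentanyl. Adjusting for such a variable can change the effect being estimated.

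**Working it through.** **Inputs.** From the documents: 120 children (Section 12), two randomised groups (Section 6). No alpha, power, effect size, SD, R² or allocation ratio is stated, so the sample size cannot be reproduced and everything below is illustrative. Assumed: 60 per arm, two-sided 5%, normal outcome with SD 1, linear model, and four independent normal baseline covariates, three sharing R² equally and one null.

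**Step 1: how often chance would pick a covariate.** With k independent characteristics tested at 0.05, the probability that at least one differs is 1 − 0.95^k. This is 18.5% for k = 4 and 26.5% for k = 6.

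**Step 2: reference difference.** The difference giving 80% power unadjusted at 60 per arm is d = 0.5157 by the t-test. The normal approximation is (1.960 + 0.842) × √(2/60) = 0.511.

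**Step 3: power.** 20,000 simulated trials per scenario. A covariate enters if its between-arm t-test p-value is below the threshold.

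| R² | Unadjusted | Selected p<0.05 | Selected p<0.50 | Fixed set | Fixed minus selected at 0.05 (points) |
|---|---|---|---|---|---|
| 0 | 80.1 | 79.7 | 78.8 | 78.7 | −1.0 |
| 5% | 80.0 | 79.8 | 80.0 | 80.6 | 0.8 |
| 10% | 80.1 | 80.0 | 81.2 | 82.5 | 2.5 |
| 20% | 80.0 | 80.7 | 84.3 | 86.9 | 6.2 |
| 30% | 79.8 | 80.9 | 86.5 | 90.8 | 9.9 |
| 35% | 80.0 | 81.1 | 87.9 | 92.7 | 11.6 |

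With the looser p<0.50 rule the loss is at most about 5 points (92.7 − 87.9 = 4.8).

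The fixed-set column can be checked by formula. The expected variance inflation from four covariates is (120 − 3)/(120 − 4 − 3) = 117/113 = 1.035, and the critical t on 114 df is 1.981. At R² 20%, SE = √(2/60 × 0.80 × 1.035) = 0.166, and power ≈ Φ(0.5157/0.1662 − 1.981) = Φ(1.12) = 86.9%. The same formula gives 78.7% at R² 0 and 92.8% at 35%.

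A different set-up leads to the same conclusion. With six covariates, one of them correlated 0.5 with the outcome, and a true difference of 0.5 SD, power is 0.78 unadjusted, 0.79 with selection at p<0.05, and 0.88 with the prognostic covariate fixed in advance.

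**Step 4: type I error, R² from 5% to 35%.**

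| Practice | Four covariates | Six covariates |
|---|---|---|
| Fixed set | 4.6–5.0% | – |
| One pre-fixed threshold (between .05 and .50) | 3.2–4.7% | – |
| Best of unadjusted and thresholds .05/.10/.20 | 5.5–6.0% | 5.8–6.2% |
| Best of all covariate subsets | 7.3–12.1% | 8.5–13.5% |

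The last row is a ceiling on what free choice could do. Monte Carlo SE is about 0.15–0.3 points for four covariates and up to about 0.4 for six (10,000 trials).

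**Step 5: a variable arising after randomisation.** The documents give no rates, so this shows only that the mechanism exists. Suppose ketorolac has no effect, rescue is correlated with pain, and rescue goes to 40% of controls and 20% of the ketorolac arm. The unadjusted difference is −0.002 SD with 4.7% type I error. Adjusting for rescue gives a spurious +0.11 SD with 8.9%. With rescue at 30% in both arms there is no bias.

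**The case against.** The clause can be read as general adjustment for patient and surgical characteristics, and Section 7 never says that its significance tests choose the covariates. On that reading the power comparison falls away. What remains is that the set is unnamed, so the model is still unspecified. The order of the section, tests of differences followed by adjustment for differences, makes the data-dependent reading the natural one.

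A mechanical threshold also does no harm to validity. It is slightly conservative, with power close to the unadjusted test. This stands: the loss is a gain not taken, and it is small when R² is 5–10%.

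The largest type I figures come from a search over all subsets that the plan does not describe. This stands too, and they should not be read as predictions.

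Every characteristic that Section 7 gives as an example is a baseline one, and the surgical term could simply mean tonsillectomy versus adenotonsillectomy. That is a fair reading, but nothing in the text confines it so. The timing issue is therefore secondary, though closing it costs nothing.

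Finally, morphine is given in two weight-based steps, with none for low scores, so the outcome is discrete and may include zeros. A normal model only approximates it, and the figures are best read as orders of magnitude.

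**Conclusion.** The concern holds. The primary model's covariates are neither named nor limited to baseline and, on the natural reading, depend on differences seen between the arms. Under the stated assumptions, selection at p<0.05 gives up about 1 point of power at R² 5%, 6 at 20% and 12 at 35% compared with a fixed set. It gains 1 point if the covariates predict nothing. These are ranges, not an estimate of this trial's loss, because the documents give no R², effect size or threshold. Type I error is not inflated by one threshold fixed in advance. It can exceed 5% if the model is chosen after results are seen, which the present wording leaves open. Any bias from adjusting for a variable arising after randomisation is possible but cannot be sized. This should be corrected; it does not undermine the design.

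**What to change.** Replace the adjustment clause in Section 7, before outcomes are compared by arm, with these statements:

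- The primary model includes a short, named set of baseline covariates chosen for expected prognostic value and used whatever the observed balance. For example: age and one measure of OSA severity, plus weight if dose is analysed in mg rather than mg/kg.
- The severity measure is AHI if it is recorded for all children. Otherwise it is the diagnosis category (sleep-disordered breathing versus OSA), if that is recorded.
- Between-arm comparisons of characteristics are descriptive and do not select covariates.
- No variable arising after randomisation enters the primary model.
- The unadjusted result is reported alongside.

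The cost is one SAP clause, a few degrees of freedom and some analytic freedom. If the chosen covariates turned out to have no prognostic value, four of them would cost about 1 point of power (78.7% against 79.7%). Age and AHI are already named in Section 7. The practical risk is missing AHI, since the inclusion criteria do not require a sleep study, so the choice of severity measure should be settled before the clause is finalised.
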